For this cluster randomized trial, we assume a Type I error rate of 0.05 and a desired power of 0.8 for the primary outcomes. Our study will include 60 microclusters (30 intervention, 30 control) with at least 8 participants in each cluster (n=480 across all clusters). We will have no fewer than 480 and can enroll up to 720. The number of participants enrolled will depend on our dynamic enrollment strategy that we've discussed already. We assume an intraclass correlation (ICC) of 0.05. For our primary outcomes (and all survey-based outcomes), we will fit a marginal model using generalized estimating equations (GEE) to estimate the effect of the intervention relative to control. Under these assumptions, we will be able to detect an intervention effect of 0.33 s.d at 80% power with 30microclusters per arm (60 total) and 8 participants per microcluster.⁹ This is a conservative estimate of power since we will adjust for the baseline value of the outcome and other covariates associated with the outcome. If we are only able to sample from 50 microclusters (25 per arm; n=400 across all clusters), we will be able to detect a moderate effect size of 0.37 s.d. at 80% power. Assuming up to 25% attrition between baseline and endline, we would still be able to detect a treatment effect of 0.31 s.d.

Statistical Analysis

Individual-level primary and secondary outcomes

For all primary and secondary outcomes drawn from our two-wave survey of 720 trial participants, we will assess differences in outcomes between the intervention and comparison groups using Generalized Estimating Equation models (GEE) that account for clustering at the study microcluster level. We will use canonical link functions for all outcomes. All models will adjust for the baseline level of the outcome, all microcluster-level characteristics used in the covariate constrained randomization (see randomization protocol),¹⁰ any individual characteristics found to be imbalanced between the intervention and control groups at baseline.

We will conduct an intention-to-treat analysis: participants that move out of (or across) study clusters, separately engage with community partner services while in the control group, or do not engage with these services while in the treatment group will all be considered exposed to their original treatment assignment.

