Second, we will estimate models that additionally include binary indicators denoting any CC who conducted interviews and fostered linkages with financial partners for each participant. Third, we will estimate a permutation inference model in which we will run our GEE models without covariates in 1,000 permutations, each of which represents a model in which treatment assignment is randomly assigned (or shuffled) 1:1 at the microcluster level (95% CIs for this method, which does not assume a specific error structure, will be constructed a the interval of estimates ranging from the 2.55th to the 97.5th percentile of the distribution of 1,000 point estimates).¹³ We will compare estimates from our main models to estimates from these uncontrolled models. Differences would suggest potential unobserved confounding. In the event of substantive differences, we will estimate bounds on the ITT effects.¹⁴ Fourth in the event of prevalent (e.g., greater than 20%) non-adherence to the intervention, we will estimate average treatment on the treated (ATT) parameters to recover causal effects of full participation in the intervention on the outcomes.¹⁵ (Given that the place-based interventions will occur without direct involvement of trial participants, non-adherence in this case would most likely to apply to the financial interventions.)

Microcluster level secondary outcomes

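### A gap between adjusted and covariate-free estimates is read as unobserved confounding and triggers bounds, although it cannot show such confounding and often arises by chance

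*Combined protocol and SAP*

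**What the plan says.** Section 9 (Statistical Analysis) fits GEE models to all survey outcomes. The main models adjust for the baseline value of the outcome, for the microcluster characteristics used in the constrained randomisation, and for any individual characteristics that turn out to be imbalanced at baseline. On the link, the plan says "We will use canonical link functions for all outcomes".

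The third of four sensitivity analyses refits the GEE models without covariates in 1,000 permutations, with treatment shuffled across microclusters. The main estimates are then compared with those from the models without covariates. The plan reads the result as follows: "Differences would suggest potential unobserved confounding". It then adds: "In the event of substantive differences, we will estimate bounds on the ITT effects". No size of difference is given for substantive, and the type of bound is identified only by a reference.

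**The concern.** Microclusters are assigned by stratified, covariate-constrained randomisation (section 8.2, Randomization). The adjusted and covariate-free models differ only in covariates that were measured. Neither contains an unmeasured variable, so the gap carries no direct information about one: a gap can appear with no confounding, and hidden bias can be present with no gap. Some covariates also enter the main model precisely because they are imbalanced, so part of any gap is built in.

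At stake is the reading of the primary result. A sound adjusted estimate could be reported with a confounding caveat and a set of bounds because of ordinary chance imbalance. Without a threshold, whether that happens can be decided after the results are seen.

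The comparator is also unclear. The models called uncontrolled are, grammatically, the fits under shuffled assignment. Those estimate zero, not the treatment effect.

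**Working it through.** **Inputs from the plan (section 9, Power Calculations).** 30 microclusters per arm with at least 8 participants each; "We assume an intraclass correlation (ICC) of 0.05"; "we assume a Type I error rate of 0.05 and a desired power of 0.8 for the primary outcomes"; and "we will be able to detect an intervention effect of 0.33 s.d at 80% power with 30microclusters per arm".

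**Assumed, not in the documents.** Two-sided tests; a baseline-to-follow-up correlation r of 0.3 to 0.7; hence a proportion R² of the variance removed by adjustment, with 25-50% as the central range.

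**1. Standard error and the plan's own figure.** Design effect = 1 + (8 - 1) x 0.05 = 1.35. Unadjusted SE = sqrt(2 x 1.35 / 240) = 0.106 SD. The detectable effect at 80% power is 0.297 (normal) or 0.302 (t, 58 df) at alpha 0.05, and 0.327 or 0.334 at alpha 0.025. The stated 0.33 therefore matches alpha 0.025, a split that the text does not state. Here 0.33 serves only as a yardstick.

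**2. What the gap is.** In a linear model with one covariate, the unadjusted minus the adjusted estimate equals the covariate's slope times the arm difference in its mean. It is a function of measured imbalance only. Under randomisation it has mean zero and SD = SE x sqrt(R²).

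- R² = 0.25: 0.106 x 0.500 = 0.053 SD. P(gap > 0.05) = 35%; P(gap > 0.10) = 6%.
- R² = 0.50: 0.106 x 0.707 = 0.075 SD. P(gap > 0.05) = 50%; P(gap > 0.10) = 18%.

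**3. Simulation check.** 4,000 cluster-randomised trials per setting, no confounding, true effect 0.33 SD, adjustment for baseline outcome only by least squares. Randomisation was simple 1:1; the baseline outcome is not one of the plan's balancing variables. Both estimators averaged 0.33, and the mean gap was at most 0.0005.

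| r | SD of gap | gap > 0.05 SD | gap > 20% of 0.33 (0.066 SD) | gap > 0.10 SD |
|---|---|---|---|---|
| 0.3 | 0.032 | 12% | 4% | 0.3% |
| 0.5 | 0.053 | 35% | 21% | 6% |
| 0.6 | 0.064 | 44% | 30% | 11% |
| 0.7 | 0.074 | 50% | 37% | 18% |

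**4. At 12 per cluster (720 adults).** Design effect = 1 + 11 x 0.05 = 1.55; SE = sqrt(2 x 1.55 / 360) = 0.093. For R² of 0.25 to 0.50 the SD of the gap is 0.046 to 0.066. P(gap > 0.05) = 28-45%; P(gap > 0.10) = 3-13%.

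**5. The literal comparator.** In 400 simulated trials with a true effect of 0.33 SD, the estimates under shuffled assignment averaged 0.00, with an average 2.5-97.5% band of -0.22 to 0.22. The unadjusted estimate under the actual assignment averaged 0.324 and fell outside its band in 85% of trials. Against this comparator, the expected difference is the treatment effect itself.

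**6. Binary secondary outcomes.** The canonical link is the logit, under which conditional and marginal odds ratios differ even with perfect balance. With a control logit of -0.85 at the covariate mean (risk 0.30), a conditional OR of 0.60 becomes a marginal OR of 0.61, 0.65 or 0.69 for a covariate SD of 0.5, 1.0 or 1.5 on the logit scale (all assumed). The two primary outcomes, the health index and the Kessler-6, are continuous. Their canonical link is the identity, which is collapsible.

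**The case against.** Four counterarguments have force.

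**Randomising clusters does not guarantee comparable participants.** Recruitment follows randomisation. Section 6 runs it to March 2024, while section 8.2 starts the visible place-based work in April 2023. The Enrollment text in section 8.2 gives a window that ends before it begins, so these dates must be reconciled. Recruiters and participants are meant to be blinded until a cluster is full, but visible street work could defeat that. Contingency referral sampling and attrition ("Assuming up to 25% attrition between baseline and endline") are other routes to systematic imbalance. This stands: a reader might infer that randomisation excludes bias, so that every gap is chance, and the documents do not support that. It does not rescue the rule. The gap still reflects only measured imbalance, which a baseline comparison shows directly, and the plan never sets it against its chance distribution.

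**The step is modest.** It is one of four sensitivity analyses, it is worded tentatively, and the bounds are additional. A reader might infer that they would displace the primary estimate; nothing in section 9 says so. This stands and limits the harm.

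**The frequencies depend on chosen cut-offs.** The plan sets none. A gap of 0.05 SD is under half the unadjusted SE and 15% of 0.33 (0.05 / 0.33), and some would not call it substantive. With a weak baseline correlation, large gaps are rare. This stands, so the size must be given as a range.

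**The bounding method cannot be judged.** It rests on a cited text that is not in the documents, so no criticism of the method is made.

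**Conclusion.** The point holds as a wrong interpretive rule, not as a flaw in the primary analysis. The comparison cannot diagnose unobserved confounding. On the natural reading (unadjusted fit, actual assignment, 8 per cluster, ICC 0.05, 25-50% of variance removed), chance alone gives a gap above 0.05 SD in about 35-50% of unconfounded trials and above 0.10 SD in about 6-18%. The figures are about 12% and under 1% at a baseline correlation of 0.3, and about 28-45% and 3-13% at 12 per cluster. On the literal reading, the rule tends to fire when the intervention works.

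The variance reduction and the cut-offs are assumptions. A reader might infer that non-collapsibility also distorts the primary comparison; it does not, because both primary outcomes use the identity link. It concerns the binary secondary outcomes only. The primary estimator, its test and the sample size are untouched.

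**What to change.** In section 9, third sensitivity analysis:

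1. Delete the sentence that reads differences as unobserved confounding, and delete this trigger for bounds.
2. Keep the permutation distribution for inference only.
3. Report the unadjusted estimate under the actual assignment as supportive, beside the pre-specified adjusted estimate. State that differences between the two reflect imbalance in measured covariates and that some difference is expected by chance.
4. For binary outcomes, compare the two on a common marginal scale, such as a standardised risk difference.
5. Tie any bounds to bias that can arise after cluster randomisation. Differential attrition already has its own test, weighting and worst-case bound in the first sensitivity analysis; differential recruitment would need to be added.

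The cost is SAP wording. No new data are needed, the permutation analysis stays, and one loosely triggered analysis is removed.

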IGNITE Kids referrals. To support enrollment efforts for the IGNITE Kids sub study, participants may also be asked if they know of and are willing to connect the study team to any families in their neighborhood with children ages 3-17. Participants will be compensated \$10 for successful referrals. Referrals for IGNITE Kids will count towards the 2-referral limit described above.

Tree referrals. To support efforts in planting at least 10 trees in each intervention microcluster, participants will be invited to refer neighbors who may be willing to receive free trees through the study. Referrals may be accepted at the time of enrollment and/or during subsequent home visit(s). Participants will be compensated \$10 for successful referrals. Participants can make and be paid for an unlimited number of tree referrals or for the amount needed until tree planting goals have been met in their particular microluster.

Intervention

Place-Based Interventions

Our suite of place-based interventions consists of four separate interventions which will all be performed simultaneously in all of the intervention microclusters. The four interventions are: vacant lot greening, tree planting, weekly trash pickup, and abandoned house remediation. The first three will be performed through the Pennsylvania Horticultural Society (PHS), while the last will be performed through the City of Philadelphia.

After microclusters have been selected and randomized to the intervention arm (n=30), we will conduct an inventory of the locations of existing vacant lots, abandoned houses, and tree canopy. All place-based interventions will start in April 2023. See below for protocol for each intervention including the intervention timeframe for each.

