Tree planting. We will plant a total of 300 trees in the intervention microclusters during this study, or roughly 10 trees per cluster. Trees will be planted between September and October 2023, with monthly watering occurring between planting and August 2024 during the growing season. We anticipate that some clusters may receive less than 10 trees and other clusters will receive more than 10 trees based on availability of planting opportunities. Trees will be planted and maintained through PHS. In Philadelphia, permission is needed from the owner of a property to plant a tree. After all participants in an intervention microcluster are enrolled and the microcluster randomization is revealed to the community coordinator team, all participants who indicated they were interested in a tree will have a tree planted in front of their residence based on the following criteria: (a) there is an open space for a tree, (b) there are no physical barriers to tree planting (eg fire hydrant), and (c) the owner of the property lives in the home and is able to give permission to plant a tree. If the participants rents the property, we will determine if they would like to seek permission from the landlord. After we determine which study participants are eligible for a tree, we will then canvas the neighbourhood microcluster to find other residents, businesses, places of worship, etc in the cluster who are not participants in the study who want a tree planted, for a total of 12-15 potential tree planting opportunities. We know that some tree planting sites will

ultimately not be eligible for planting which is why we will initially select 12-15 sites with the aim of planting 10 trees per cluster. This list will then be sent to the PHS who will work with the City of Philadelphia to determine which physical locations are eligible for a tree. For example, sometimes there are water lines too close to the side-walk surface that make a location ineligible.

Trash cleanup. We will provide weekly trash cleanup in all public spaces in the blocks included in our intervention clusters between April 2023 and August 2024. Public space includes on streets and sidewalks, but not into private front yard space. Although the city performs weekly trash pickup, this is limited to trash that is in garbage cans, leaving neighborhoods with a significant trash burden that does not fall under the purview of regular sanitation. Trash cleanup will occur through PHS.

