The rationale for providing these services as part of this study follows from a large literature linking economic and financial security to health and well-being.^{4–6} While these services are generally available to all Philadelphians, informational and time constraints (current models of delivery require individuals to reach out to ask for services) and budgetary constraints on the partner side remain barriers to engagement. The goal of the financial intervention in this study is to increase access to these services by increasing financial capacity among the partner organizations and reducing barriers among potential beneficiaries.

The intervention group will be provided the above package of financial services using the following general approach. Within one month of enrollment and completing the baseline survey, the research team will contact intervention group participants, provide information on each of the financial partners, as well as a checklist for

financial documents needed to have on hand to work with each partner. At that time, intervention group participants will select a pre-filled appointment slot with the Clarifi team for their initial intake. This appointment can either be in-person or virtual, depending on the participant's preference. Intervention group participants will receive text-message reminders in advance of their initial appointment, as well as a follow up text to assess whether they attended the appointment after the intended date and time. In the event participants were unable to participate, the research team will reschedule the initial session and again confirm participation via text-message. Participants will be eligible to receive their one-time \$400 at this initial session, which will be delivered in the form of a check or direct deposit based on participant preference. After this initial meeting, the research team will help participants schedule a second appointment (and any subsequent appointments, as needed), following the same strategy.

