After connecting participants with the Clarifi team, participants will then be directly connected to BDT and CFW using a similar approach. BDT provides a screening tool that determines which benefits individuals are eligible for. The CC team will set up a time based on the participants' availability to complete this screening process with them in person. the participants have completed the screening process, they will call the phone line that BDT created for our study where a BDT representative will then walk the participants through the application process for benefits.

CFW provides both virtual and in-person (at several dedicated locations in the city) tax preparation services. Participation in these services will be confirmed in the same manner as the Clarifi services with the CC providing pre-selected appointment slots to the participants.

By the end of the intervention period in August 2024, the goal of the financial intervention will be for intervention group participants to have worked with a Clarifi counsellor at least 2 times and to have received a one time \$400 cash grant, completed the benefits screening, application and follow-up process with BDT one time, and filed income taxes with CFW.

At the end of the intervention period, participants in the control group will receive a list comprising of each of the financial partners and their contact information, but will not receive the further engagement and support to enroll in these services; nor will they receive the \$400 cash grant. Provision of information to this group goes one step beyond current outreach efforts by the financial partners, which include direct mailers and advertising.

9. Analysis plan

Outcome Measures

The primary and secondary outcomes for this study are described in detail **Table 1**. Primary outcomes will be drawn from our two-wave survey of study participants (one baseline wave and one endline wave); our secondary outcomes will be drawn from the same survey as well as from key administrative data sources (detailed in **Table 1**).

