Our two primary outcomes will focus on (1) overall health and (2) psychological distress. Our measure of overall health comes from an index based on responses to three survey questions: a self-reported rating of the participant's general health (on a 5 point Likert scale, ranging from poor to excellent); the self-reported number of days in the last 30 in which poor physical or mental health precluded engagement in the participant's usual activities; and a self-reported rating change in overall health outcomes over the last 12 months (three point scale denoting worse, same, or better). We will use the method of Anderson (2008) to create a single (standardized) index of overall health.⁷ This method uses the inverse covariance matrix of the variables to create the index and allows for missing observations.

Our measure of psychological distress is the Kessler-6 scale, a validated measure of non-specific psychological distress represented by the summed score of six questions querying the frequency of symptoms of feeling nervous, hopeless, depressed, restless, depressed, that everything was an effort, and worthless over the past 30 days.⁸ The Kessler-6 ranges from 0-24.

Secondary child health outcomes

In addition to the outcomes listed above, we plan to evaluate a series of secondary outcomes focused on child health and well-being, derived from a follow-up survey administered to participants with children ages 3 to 17 at the time of 24-month follow-up. These will include caregiver-reported child health, health care utilization, and several outcomes related to child well-being, neighborhood safety for children, and parenting, as listed in Table 2.

We will also examine additional child health outcomes for all children residing in IGNITE study clusters using secondary analysis of existing data sets. Specifically, we will assess school attendance and performance for all cluster residents using Philadelphia school district data, birth outcomes for cluster residents using Pennsylvania birth certificate data, and health care utilization outcomes for all cluster residents using electronic health record data from the Children's Hospital of Philadelphia. These outcomes are also included in Table 2. We will obtain separate approval from the Children's Hospital of Philadelphia Institutional Review Board prior to abstraction of electronic health record data for these child health outcomes.

Power Calculations

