accessing major public benefits or who had not filed tax returns prior would be more likely to benefit from financial interventions than those already engaged with these activities. Similarly, individuals living in study clusters with relatively larger numbers of abandoned lots, fewer trees, or more abandoned homes would stand to benefit more from the environmental interventions than those who did not. Formally, we will estimate versions of our main GEE models for the primary outcomes in which we will include interactions between the treatment indicator and binary indicators for individuals participating in fewer than sample median number of public benefit programs; not filing (or had someone file on their behalf) a tax return in the previous year; being below the median of the household financial security scale; living in a microcluster below the median in terms of tree canopy; living in a microcluster that is above the median in terms of the number of abandoned lots; and living in a microcluster that is above the median in terms of the number of houses. Positive and statistically significant coefficients on these interaction terms would provide suggestive evidence that the specific intervention that would address the pre-intervention attribute in question helped drive treatment effects. For example, a positive and significant coefficient on the interaction between treatment and living in a cluster with above the median numbers of abandoned lots would suggest that abandoned lot remediation played a role in driving overall treatment effects. Interpretation of these coefficients requires knowledge of actual exposure to treatments; e.g., it would be more credible to conclude that provision of tax preparation services helped drive health outcomes if large numbers of intervention group participants reported using these services.

Primary Outcomes				
Outcome	Measure	Data Source	Type of Data	Timeframe
Overall Health Index	Composite index using method of Anderson (2008) based on three questions: rating of overall health (5-pt Likert ranging from poor to excellent); rating of how health has changed in last 6_months (better, same, worse); and number of days in the last 30 where physical or mental health precluded engagement in usual activities (self-care, work, recreation); (Oregon HIE)	Survey	Continuous (index)	Baseline, 24 months
Psychological distress	Kessler-6	Survey	Continuous (scale)	Baseline, 24 months
	Secondary Out	comes		

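### The planned ATT cannot be said to recover the effect of full participation, because participants who skip the financial services still live with the place-based work

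*Combined protocol and SAP*

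**What the plan says.** The fourth sensitivity analysis in section 9 (Statistical Analysis) is triggered by prevalent non-adherence, with above 20% as the example. In that event, "we will estimate average treatment on the treated (ATT) parameters to recover causal effects of full participation in the intervention on the outcomes". A textbook is cited. The text names no estimator, ties no adherence definition to the analysis and states no identifying assumption. The sentence that follows observes that place-based work does not need participants to take part, so "non-adherence in this case would most likely to apply to the financial interventions".

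Section 8.2 (Place-Based Interventions) describes "four separate interventions which will all be performed simultaneously in all of the intervention microclusters". Under Trash cleanup it adds: "We will provide weekly trash cleanup in all public spaces in the blocks included in our intervention clusters". Neither depends on whether a resident uses a financial service.

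On the financial side, section 8.2 sets a goal for the end of the intervention period: at least two Clarifi sessions, the $400 grant, the benefits process with BDT once, and a tax filing with CFW. The grant is available at the first Clarifi session. The ITT paragraph of section 9 foresees that some controls may use the partner services on their own.

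**The concern.** The claimed property and the remark that follows it pull apart. Someone in the intervention arm who never meets a financial partner still lives on blocks due for trash cleanup and, where sites allow, lot greening, tree planting and house remediation. That person is partly treated, and an adherence-scaled estimate treats them as untreated.

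The plan gives no reason to think that this partial exposure has no effect. The Background links both dilapidated surroundings and economic insecurity to poor health. Under Evaluating Mechanisms, residents of clusters with more abandoned lots, fewer trees or more abandoned homes "would stand to benefit more from the environmental interventions than those who did not". A zero effect on non-adherers is possible, but it runs against the trial's own reasoning.

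At stake is the meaning of a figure that the plan describes as causal. For a given effect on non-adherers, the discrepancy grows as adherence falls, and low adherence is what triggers the analysis.

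**Working it through.** The plan gives no ATT figure, so there is none to reproduce. The check is algebraic, with assumed values for scale.

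**Inputs**
- c: share of adherers in the intervention arm. The plan's example trigger of 20% non-adherence corresponds to c = 0.8; c = 0.6 is an assumption.
- E: package effect in adherers, which is the quantity the ATT is meant to give.
- P: average effect of assignment on non-adherers. The documents do not give it. It contains the place-based work. If adherence means the full financial goal in section 8.2, it also contains any partial financial receipt, such as one session with the grant.
- ITT = 0.33 SD: the detectable effect quoted under Power Calculations, used here only as a scale.
- No uptake in controls, effects additive, outcome oriented so that benefit is positive.

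**Formulas**
1. ITT = cE + (1 - c)P.
2. Scaled value: ITT/c = E + P(1 - c)/c.
3. Discrepancy: ITT/c - E = P(1/c - 1). It is zero only if P = 0 or c = 1.
4. Rearranged: E = (ITT - P(1 - c))/c.

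**Numbers**

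| c | Scaled value (0.33/c) | P | E = (0.33 - P(1 - c))/c | Scaled relative to E |
|---|---|---|---|---|
| 0.8 | 0.4125 | 0 | 0.4125 | 0% |
| 0.8 | 0.4125 | 0.165 | (0.33 - 0.033)/0.8 = 0.371 | +11% |
| 0.8 | 0.4125 | 0.33 | (0.33 - 0.066)/0.8 = 0.33 | +25% |
| 0.6 | 0.55 | 0 | 0.55 | 0% |
| 0.6 | 0.55 | 0.165 | (0.33 - 0.066)/0.6 = 0.44 | +25% |
| 0.6 | 0.55 | 0.33 | (0.33 - 0.132)/0.6 = 0.33 | +67% |
| 0.6 | 0.55 | -0.0825 | (0.33 + 0.033)/0.6 = 0.605 | -9% |

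Check of one row: E = 0.44, P = 0.165, c = 0.6 gives ITT = 0.264 + 0.066 = 0.33. The discrepancy is 0.55 - 0.44 = 0.11, which equals 0.165 × (1/0.6 - 1).

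The percentages depend only on c and on P as a fraction of the ITT, so another ITT would leave them unchanged at the same fraction. P refers to non-adherers alone and should not be read as the place-based share of the ITT. At c = 0.8, P = 0.165 contributes 0.2 × 0.165 = 0.033, which is 10% of 0.33.

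**The other route.** Comparing adherers with all controls does not need P = 0. But adherers select themselves and have no identified counterpart in the control arm. The comparison then rests on no unmeasured confounding of uptake, which the plan does not state either.

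**The case against.** The plan never says that it will divide by adherence. It names a parameter and cites a source, so a bias in an unnamed estimator has not been demonstrated. That is fair, and the figures above are conditional on scaling. It does not rescue the claim, because the other obvious route gives up randomisation.

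The plan is not silent on what full participation means: the four-part goal in section 8.2 is the natural reading. This stands, although the goal is not tied to the ATT. Adopting it would make exclusion harder to defend, since people who fall short of it may already hold the grant.

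Exposure to place-based work is not uniform. The City may refuse some lots, tree numbers vary with planting sites, and some participants move. P could therefore be small, zero or even negative.

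A reader might infer that the ATT is certain to exaggerate the benefit, or that the trial's main result is compromised. The documents support neither. The sign of the discrepancy follows P, which is unknown, and the primary analysis is an ITT in which non-engagers stay in their assigned arm. In much of the range shown, the discrepancy may also be smaller than the sampling error. That keeps the severity low, but a larger sample would not remove the discrepancy.

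**Conclusion.** The concern holds as a low-severity point. The statement that the ATT recovers the effect of full participation is not supported under either obvious estimator. Scaling needs a zero effect of assignment on financial non-adherers, which is unstated and implausible on the plan's own rationale. Comparing adherers with controls is no longer a randomised comparison.

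Under scaling the discrepancy is P(1/c - 1). With an assumed ITT of 0.33 SD and P between 0 and 0.33, a reported 0.41 SD at c = 0.8 would stand against a true 0.41 down to 0.33. At c = 0.6, a reported 0.55 SD would stand against 0.55 down to 0.33. These ranges assume additive effects and no control uptake, and P and the lower adherence value are illustrative. They show how far the label could mislead and do not predict a bias.

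**What to change.** Keep the ITT as the effect of the package, and delete the statement that the ATT recovers the effect of full participation. If a scaled figure is still wanted:

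- Define adherence in advance as any uptake of the study's financial package in the intervention arm. Partial receipt, including the grant, then counts as uptake. Say openly that this differs from the full-completion goal in section 8.2.
- Use the participant-level tracking already planned. For Clarifi this is "a follow up text to assess whether they attended the appointment after the intended date and time". For CFW, "Participation in these services will be confirmed in the same manner as the Clarifi services". The community coordinators complete the benefits screening with participants in person. Partner-held data will not serve, because Evaluating Mechanisms says they are aggregate and cover the treatment group only.
- State the exclusion assumption. Report (ITT - P(1 - c))/c over plausible values of P, with P = 0 as one extreme.
- Compute it on a mean-difference or risk-difference scale, where the additive formula applies.
- Label the result as the effect of the package, relative to usual access, in those who take up the financial services. If control-arm use of the partners is measured, describe it alongside. Do not treat it as the same treatment, since controls get neither the grant nor help with scheduling.

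The cost is a change of wording to one conditional analysis. The downside is a range in place of a single ATT figure.
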